APPENDIX B: ADVERTISEMENTS

Radio Advertisement:

Do you smoke marijuana/cannabis? Is it interfering with work or school? If you want to quit using marijuana you may be eligible for a paid research study. A research clinic at (study site) is studying a medication that may help people quit marijuana/cannabis, (IRB number). If you are male or female, between the ages of 18 and 60, smoke marijuana/cannabis, and want to quit, please call us at (phone number). All calls and information gathered are confidential. Again that's (phone number).

Online Advertisement:

Title: SMOKE MARIJUANA/CANNABIS? Want to quit? Do you smoke marijuana regularly and want to quit? A research group at __(study site)__ is running a paid clinical trial investigating a medication designed to help with the symptoms of marijuana withdrawal. Participants must be:

- Ages 18-50
- In good physical and mental health
- Willing to try quitting marijuana/cannabis for eight weeks

Participants must NOT be:

Abusing any other drugs or alcohol

If you would like to try quitting marijuana/cannabis and want more information about this study, please call us at (XXX) XXX-XXXX All information is kept confidential. IRB # XXXXXXXXXXX

Mini-Flier Advertisement:

Want to quit smoking marijuana? Earn up to \$1,265

Paid Volunteers needed for a (study site) study investigating a medication designed to increase the brain's own marijuana like chemical

For more information call: (XXX)-XXX-XXXX All calls are confidential

IRB # XXXXXXXXXXX ____(study site)____

Full Page Advertisements:

VOLUNTEERS NEEDED Men and Women ages 18-60 who use marijuana (cannabis) needed for a clinical trial! Earn up to \$1,265 Call (XXX)XXX-XXXX

All calls are confidentia

Want to quit smoking marijuana? Earn up to \$1,265

Paid Volunteers needed for a __(study site)__ study investigating a medication designed to increase the brain's own marijuana like chemical

For more information call: (XXX)-XXX-XXXX All calls are confidential

IRB # XXXXXXXXXXX __(study site)__

Want to quit smoking marijuana? Earn up to \$1,265

Paid Volunteers needed for a __(study site)__ study investigating a medication designed to increase the brain's own marijuana like chemical

For more information call: (XXX)-XXX-XXXX All calls are confidential

> IRB # XXXXXXXXXXX __(study site)__

Want to quit smoking marijuana? Earn up to \$1,265

Paid Volunteers needed for a (study site) study investigating a medication designed to increase the brain's own marijuana like chemical

For more information call: (XXX) XXX-XXXX All calls are confidential

Page **104** of **116** APPROVED BY THE YALE UNIVERSITY IRB 5/1/2022

APPENDIX C: PHONE SCREEN QUESTIONNAIRE

Read Verbatim to Participant:

"We would like to ask you some general information to determine whether you might qualify for studies at our research group. This information will only be used to determine your eligibility to participate in research. This information will be stored in secure research files. If you do not want any information about you stored, we will terminate this interview now. If you agree to proceed ahead with this preliminary interview and seem to be eligible to participate in this study, we may invite you for a face to face meeting. Would you like to continue?"

YES	Ι	Ν	0
-----	---	---	---

Name (First Last):		
		Gender:
Phone #1:	Phone Type: _	
Phone #2:	Phone Type: _	
Email Address:		
Preferred contact? Phone #1	/ Phone #2 / Email Add	Iress
Highest level of education:		
What race do you identify with	1:	
Are you currently participating Blood, etc): YES / NO	in research or within the	he past 30 days (Details: Where, Meds,
Can we keep your information	on filo to bo oblo to or	antant you for future studios: VES / NO
		intact you for future studies. TES / NO
Are you currently participating in research or within the past 30 days (Details: Where, Meds, Blood, etc): YES / NO Can we keep your information on file to be able to contact you for future studies: YES / NO Are you currently working? YES / NO If yes, current job: How long at current job: If no, why: Do you have a flexible Schedule: YES / NO		
If no, why:		
Do you have a flexible Sched	ule: YES / NO	
Do you use marijuana/cannab	is: YES / NO	
How often do you typically use	e	
marijuana/cannabis:		
How much do you spend per		
How long have you smoked a	t this rate:	

Would you say that marijuana/cannabis is your primary drug of choice (or do you like to use anything else with marijuana/cannabis)? Yes / No

About how many drinks do you have a week? What days do you typically drink? What types of alcohol do you consume? (determine alcohol for the month):

Date of your last drink:

How many drinks did you have:

Has alcohol ever been a problem for you: YES / NO Have you ever had a DWI: YES / NO

Have you used any other street drugs in the past 3 months? (MJ, Salvia, Spice, Cocaine, Heroin, Speed, Hallucinogens, prescription meds recreationally? etc.): Yes / No

Can you remember the last time you quit smoking even if it was just for a few days or weeks (why, when, how long, etc.)

What street drugs have you used over your lifetime? (MJ, Salvia, Spice, Cocaine, Heroin, Speed, Hallucinogens, prescription meds recreationally, etc.)?

Drug	Date of last use	Time period of Heaviest Use	Frequency (daily, weekly)	Approx amount per use (gram, oz., joint, # pills)

How much caffeine do you have per day?

Do you currently smoke or use tobacco: Yes / No

How much tobacco do you currently use:_____

Were you ever a cigarette smoker? Yes / No When and how much did you use?:_____

Do you have any medical problems right now: Yes / No

Do you use any prescription or over the counter medication or vitamins or supplements (type and duration)?

Do you have diabetes: Yes / No

Any Surgeries: Yes / No (what and when) _____

Any seizures or fainting spells: Yes / No

Are you allergic to any medications? Yes / No

Are you allergic to any food? Yes / No

Have you had any medical problems in the past: Yes / No If yes, please specify:

Head (Such as: Head Injury? Loss of consciousness or Infection of the brain?)

Heart (Such as: Heart Attack or Heart disease?)

Lungs or Asthma (Such as: Lung disease?)

Liver (Such as: Liver disease?)

Kidney (Such as: Kidney disease?)

Stomach (Such as: Intestinal problems?)

Circulatory (Such as: High blood pressure?)

APPROVED BY THE YALE UNIVERSITY IRB 5/1/2022

Have you given any blood donations recently: Yes / No When: _____

Any other medical issues or important things that we should be aware of?

Have you ever seen a counselor or therapist: Yes / No

If yes, please explain (Duration, Diagnosis, Time-period, Meds, problem resolved?):

Have you ever been hospitalized for any psychiatric, mental, or emotional problems: Yes / No If yes, please explain (when, how long, how close to event):

Notes:_____

APPENDIX E: INCLUSION / EXCLUSION CRITERIA CHECKLIST

1.	Ages 18-60 years, inclusive (age verified picture identification).	Yes 🗌 No 🗌
2.	Male or Female.	Yes 🗌 No 🗌
3.	Individuals with DSM-V criteria for CUD of at least moderate severity (≥ 4 [of 11] symptoms).	Yes 🗌 No 🗌
4.	Current cannabis consumption greater than or equal to 30 joints/month (approximately daily) over the past 3 months	Yes 🗌 No 🗌
5.	Positive for urinary THC-COOH on two separate occasions during screening (> 50ng/ml).	Yes 🗌 No 🗌
6.	Primary drug of choice cannabis.	Yes 🗌 No 🗌
7.	Must express a willingness at screening to set a date within the first week of randomization to attempt to quit using cannabis.	Yes 🗌 No 🗌
8.	Physically healthy i.e., no clinically unstable medical conditions at the discretion of the investigator.	Yes 🗌 No 🗌
9.	Have given written informed consent, and have capacity to consent and comply with study procedures.	Yes 🗌 No 🗌
10	Must be able to read English as per the judgment of the site investigators. Participants are required to be able to read because there are several self-administered measures that they must read, understand and provide written answers.	Yes 🗌 No 🗌
11	Must provide the name of at least 1 contact (preferably 2), who would assist study staff in locating them during the study period.	Yes 🗌 No 🗌
12	For women of childbearing potential (WOCBP) and men, willingness to practice birth control and to inform study staff immediately if either they (for women) or their partner (for men) becomes pregnant.	Yes 🗌 No 🗌
13	Must be willing to complete a number of study assessments and procedures remotely.	Yes 🗌 No 🗌

INCLUSION CRITERIA

EXCLUSION CRITERIA

1.	Clinically significant unstable medical disorders (as determined by the site investigator) that will increase potential risk or interfere with study participation e.g., ongoing seizure disorder, uncompensated congestive heart failure, uncontrolled severe diabetes, uncontrolled severe hypertension, etc.	Yes 🗌 No 🗌
2.	Laboratory tests with clinically significant abnormalities (as determined by the site investigator)	Yes 🗌 No 🗌
3.	Positive urine toxicology screen for another drug with clinical evidence of use disorder for that drug (with the exception of THC-COOH at screening).	Yes 🗌 No 🔲
4.	Pregnancy by history and or laboratory confirmation (serum HCG).	Yes 🗌 No 🗌
5.	Lactation.	Yes 🗌 No 🗌
6.	Other DSM-5 substance use disorder in the past three months (excluding cannabis, nicotine, caffeine, and mild alcohol use disorder [≤ 3 criteria]).	Yes 🗌 No 🗌
7.	Physiological dependence on another prescribed (e.g. benzodiazepine), not prescribed licit (e.g. alcohol or benzodiazepine) or illicit substance	Yes 🗌 No 🗌

	(e.g. opioid) requiring medical management, such as alcohol, opioids, or benzodiazepines, excluding caffeine, and nicotine.	
8.	Abstinence from cannabis for more than 1 week at the time of randomization.	Yes 🗌 No 🗌
9.	Meeting DSM-5 criteria for current serious mental illness (e.g., major depression, bipolar disorder, schizophrenia, any psychotic illness, including substance-induced psychosis, and current substance-induced mood disorder. Individuals who meet criteria for current major depression at a mild severity may be included at the discretion of the site principal investigator.	Yes 🗌 No 🗌
	Lifetime history of DSM-5 bipolar disorder or any psychotic disorder.	Yes 🗌 No 🗌
11	Meeting DSM-5 criteria for any psychiatric disorder that may, according to the investigator's judgment, require initiation of a pharmacological or non-pharmacological intervention over the course of the study.	Yes 🗌 No 🔲
12	Taking psychotropic medication/s that could interfere with interpretation of the study results or interact with study medication. Includes but is not limited to opioid analgesics, sedative hypnotics, or other known CNS depressants, etc. Exceptions include preexisting treatment with sleep agents, antidepressants for preexisting stable insomnia or depression, respectively.	Yes 🗌 No 🗌
13	Current moderate risk for suicide as measured by the Columbia Suicide Severity Rating Scale (CSSRS) suicidal ideation (in the last month) score of greater than 2 and a history of recent (past 1 year) serious suicide attempt (lethality score of >2 on CSSRS).	Yes 🗌 No 🗌
14	Current or past history of significant violence (past 2 years).	Yes 🗌 No 🗌
15	Currently in a residential treatment setting in which substance use is monitored and restricted, since the restricted access to drugs could represent an important confounding variable.	Yes 🗌 No 🔲
	Participants who, in the investigator's opinion, would be unable to comply with study procedures or assessments, or would be unacceptable study candidates (e.g., poses threat to staff).	Yes 🗌 No 🗌
17	Participation in a clinical trial and receipt of investigational drug(s) during past 30 days.	Yes 🗌 No 🗌
18	Known allergy to FAAH-inhibitors	Yes 🗌 No 🗌
19	Co-medication with CYP3A inhibitor, CYP3A inducers, or P-glycoprotein substrates, within 48 hours or 5 half-lives prior to baseline, at the discretion of the site investigator	Yes 🗌 No 🗌

Eligible: Y / N

PI Signature: _____

Date: ___ / ___ / ____

APPROVED BY THE YALE UNIVERSITY IRB 5/1/2022

APPENDIX F: COLLATERAL CONTACT QUESTIONNAIRE

Date: ___ / ___ / ____

Collateral Contact Name: _____

Phone Number: (____) ____ - ____

Relationship to Participant: _____

Dear _____,

(participant) is being considered for a research study at our center. To qualify for the study, participants are expected to be free of any medical or psychiatric history. (participant) has identified you as a reliable source of information. (participant) has signed a release of information to permit us to contact you.

To the best of your knowledge, does _____ have any history of mental illness? Y / N

If yes, please explain:_____

To the best of your knowledge, does (participant) have any history of medical problems? Y / N

If yes, please explain:

To the best of your knowledge, does (participant) have any history of substance abuse problems with marijuana/cannabis? Y / N

To the best of your knowledge, does (participant) have any history of substance abuse problems with any substance other than marijuana/cannabis (i.e. alcohol, cocaine, heroin, etc.)? Y / N

To the best of your knowledge, is there any reason (participant) should not participate in a research study? Y / N

If yes, why not?

Thank you for your time.

Sincerely,

(site principal investigator)

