6.0 STUDY POPULATION

6.1 Inclusion Criteria: Participants must meet all of the following inclusion criteria to be eligible for enrollment into the study:

- 1) Ages 18-60 years, inclusive (age verified using one form of picture identification with date of birth).
- 2) Male or Female.
- Individuals with DSM-V criteria for CUD of at least moderate severity (≥ 4 [of 11] symptoms).
- 4) Current cannabis consumption greater than or equal to 30 joints/month (approximately daily) over the past 3 months
- Positive for urinary THC-COOH on two separate occasions during screening (> 50ng/ml).
- 6) Primary drug currently being used is cannabis.
- 7) Primary method of cannabis consumption (>80% of the time) is smoking cannabis.
- Must express a willingness at screening to set a date within the first week of randomization to attempt to quit using cannabis.
- 9) Physically healthy i.e., no clinically unstable medical conditions at the discretion of the investigator.
- 10) Have given informed consent, and have capacity to consent and comply with study procedures.
- 11) Must be able to read English as per the judgment of the site investigators. Participants are required to be able to read because there are several self-administered measures that they must read, understand and provide written answers.
- 12) Must provide the name of at least 1 contact (preferably 2), who would assist study staff in locating them during the study period.
- 13) For women of childbearing potential (WOCBP) and men, willingness to practice birth control and to inform study staff immediately if either they (for women) or their partner (for men) becomes pregnant.
- 14) Must be willing to complete a number of study assessments and procedures remotely.

6.2 Exclusion Criteria: Participants presenting with any of the following exclusion criteria will be excluded from participation:

- Clinically significant unstable medical disorders (as determined by the site investigator) that will increase potential risk or interfere with study participation e.g., ongoing seizure disorder, uncompensated congestive heart failure, uncontrolled severe diabetes, uncontrolled severe hypertension, etc.
- 2) Laboratory tests with clinically significant abnormalities (as determined by the site investigator)
- 3) Positive urine toxicology screen for another drug with clinical evidence of use disorder for that drug (with the exception of THC-COOH at screening).

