- 4) Pregnancy by history and or laboratory confirmation (serum HCG).
- 5) Lactation.
- 6) Other DSM-5 substance use disorder in the past three months (excluding cannabis, nicotine, caffeine, and mild alcohol use disorder [≤ 3 criteria]).
- 7) Physiological dependence on another prescribed (e.g. benzodiazepine), not prescribed licit (e.g. alcohol or benzodiazepine) or illicit substance (e.g. opioid) requiring medical management, such as alcohol, opioids, or benzodiazepines, excluding caffeine, and nicotine.
- 8) Abstinence from cannabis for more than 1 week at the time of randomization.

- Meeting DSM-5 criteria for current serious mental illness (e.g., major depression, bipolar disorder, schizophrenia, any psychotic illness, including substance-induced psychosis, and current substance-induced mood disorder.)
 - a. Individuals who meet criteria for current major depression at a mild severity* may be included at the discretion of the site principal investigator.
 * Per the DSM-5, current major depression at a mild severity is defined as: "Few, if any, symptoms in excess of those required to make the diagnosis are present, the intensity of the symptoms is distressing but manageable, and the symptoms result in minor impairment in social or occupational functioning."(228)
- 10) Lifetime history of DSM-5 bipolar disorder or any psychotic disorder.
- 11) Meeting DSM-5 criteria for any psychiatric disorder that may, according to t he investigator's judgment, require initiation of a pharmacological or non-pharmacological intervention over the course of the study.
- 12) Taking psychotropic medication/s that could interfere with interpretation of the study results or interact with study medication. Includes but is not limited to opioid analgesics, sedative hypnotics, or other known CNS depressants, etc. Exceptions include preexisting treatment with sleep agents, antidepressants for preexisting stable insomnia or depression, respectively.
- 13) Current moderate risk for suicide as measured by the Columbia Suicide Severity Rating Scale (CSSRS) suicidal ideation (in the last month) score of greater than 2 and a history of recent (past 1 year) serious suicide attempt (lethality score of >2 on CSSRS).
- 14) Current or past history of significant violence (past 2 years).
- 15) Currently in a residential treatment setting in which substance use is monitored and restricted, since the restricted access to drugs could represent an important confounding variable.

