9.2 Informed Consent Procedures: The consent process is a multistep process, whereby information about the risks and benefits of the study will be provided to potential participants. Participants will be required to read the informed consent form and the investigator or her/his designee will additionally describe the risks and discomforts. The consent process may be completed remotely or in person. As part of the consenting process, one form of picture identification with date of birth will be copied and kept on file to verify the participant meets age inclusion requirements. Once all screening procedures have been collected, research staff as well as the principal investigator will review all relevant information and determine, based on the inclusion and exclusion criteria, if the participant will continue with the remaining study procedures.

To ensure that the study participant understands the study, the participant will be asked questions about the study procedures and the risks associated with participation. Participants will be asked to pass a study questionnaire to document their understanding of the study. This consent questionnaire is located in Appendix D. If any concern arises that the study participant did not fully understand the study, the principal investigator (PI) or her/his designee may decide that the participant is not suitable for participation. If the participant is still interested after all questions have been answered, the PI will ask the participant to sign the informed consent form. Any participant who appears incapable of providing informed consent will be excluded.

9.3 Contact/Informant: As a requirement for entry into this study, participants will need to identify an individual who is can serve as a contact and as a collateral source of information. Or two people could serve in these roles. A family member or a significant other/spouse is preferred. The participant will need to sign a hospital approved release of information to permit the study team to contact the individual. The contact/informant could be contacted to locate the participant during the study. The contact/informant will also be contacted to provide collateral

information that will be used to determine the participant's eligibility (Appendix F). Furthermore, the contact/informant may help corroborate information provided by the participant which in turn will enhance the reliability of the information, as described elsewhere (204).

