10.4.1 Documentation of Concomitant Medication: Concomitant medication is any drug given in

addition to the study drug. These may be prescribed by a physician or obtained by the participant over the counter. Concomitant medication is not provided by the Coordinating Center. At each study visit, participants will be asked whether they have taken any medication other than the study drug (used from signing of informed consent through the end of the study), and all medications including vitamin supplements, over-the-counter medications, and oral herbal preparations, must be recorded in the source documents. Permitted concomitant medications will be left to the direction of the site principal investigator. When in doubt the site investigator should contact the overall medical monitor or the study principal investigator to discuss.

10.4.2 Documentation of Concurrent Medical Conditions: Concurrent medical conditions are those significant ongoing conditions or diseases that are present at signing of informed consent. This includes clinically significant laboratory, ECG, or physical examination abnormalities noted at screening, according the judgment of the investigator. The condition (i.e., diagnosis) should be described.

Participants with stable, chronic, nonemergent, well-controlled conditions may be permitted to participate at the discretion of the site investigator. Conditions that will be excluded: 1) serious or acute conditions e.g., appendicitis, 2) conditions that require frequent and significant medical interventions e.g., sickle cell crisis, 3) conditions that interfere with the primary outcome of interest e.g., alcohol or nicotine withdrawal, intoxication or dependence, etc. When in doubt the site investigator should contact the overall medical monitor or the PI to discuss.

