10.4.3 Documentation of Concurrent Psychiatric Conditions: Concurrent psychiatric conditions are those significant ongoing psychiatric conditions that are present at the signing of informed consent. Any concurrent psychiatric conditions should be well documented at screening. Participants with stable, chronic, nonemergent, well-controlled psychiatric conditions may be permitted to participate at the discretion of the site investigator e.g., anxiety disorder. Conditions that will be excluded: serious, acute conditions e.g., acutely suicidality, or conditions that require frequent and significant medical interventions e.g., bipolar disorders, conditions that interfere with the primary outcome of interest e.g., alcohol or nicotine withdrawal, intoxication or dependence, etc. When in doubt the site investigator should contact the overall medical monitor or the PI to discuss.

Disallowed psychiatric problems include: a) Schizophrenia Spectrum and other Psychotic disorder in lifetime (current or past), b) Bipolar or related disorder in lifetime (current or past), and c) current Major Depressive Disorder.

10.5 Structured Clinical Interview for DSM-5: to diagnose any significant psychiatric disorders (210).

10.6 Psychiatric Research Interview for Substance and Mental Disorders (PRISM): is a semi-structured diagnostic interview designed to deal with the problems of psychiatric diagnosis when participants drink heavily or use drugs. This interview will help differentiate between primary disorders, substance-induced disorders, and the effects of intoxication and withdrawal.

For training and quality control purposes, the PRISM interviews will be audio recorded. The interviewees' Subject ID number and the study visit week that the interview is being conducted at will be stated at the beginning of the recording. The participants name will not be included in the recording. Participants will be asked at screening if they are willing to consent to the audio recording being conducted. If the participant does not consent to this, the PRISM interview will still be conducted, but will not be audio recorded. The audio recordings will be transferred to [name] at Columbia University for training and quality control purposes via each site's IRB approved method of data transfer.

10.7 *Fagerstrom Test for Nicotine Dependence (FTND)*: will be used to estimate nicotine dependence (211).

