11.3 Assessment of Potential Risks and Benefits: Cannabis is the most widely used illicit substance worldwide. In 2009, cannabis was the illicit drug with the highest rate of past year dependence or abuse; there were more treatment admissions for cannabis in the US than for any other drug including cocaine or heroin. There are no approved pharmacological treatments for CUD and as stated in the FOA: *"the development of safe and effective medications to treat these disorders is an urgent public health need."* Furthermore, in keeping with the expectation stated in the FOA the proposed study represents a collaboration with the pharmaceutical industry.

In the completed phase 2A study, PF-04457845 reduced cannabis withdrawal, reduced selfreported cannabis use, reduced urinary levels of THC-COOH and restored stage 3 sleep deficits in cannabis dependent individuals with an excellent tolerability and safety profile. For the proposed study, the potential risks to participants appear low. Furthermore, the study entails no financial or social risk to the participant.

FAAH inhibitors are a new chemical entity. There are very few FAAH-inhibitors that are available for use in humans, and none are available commercially. The proposed study has the potential to yield important knowledge towards continued development of this treatment approach for an unmet need. Therefore, the proposed study has a favorable risk/benefit profile.

11.4 Mitigation of Risk:

11.4.1 Screening: For the proposed study, participants will be carefully screened to exclude participants with any significant medical or psychiatric problems. The screening process is rigorous and includes a structured clinical interview for DSM, a psychiatric and medical evaluation by a psychiatrist, laboratory tests, EKG, etc. An outside informant specified by the participant will be contacted to confirm the history. This process should screen out unsuitable participants.

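### Appendix F tells the informant that participants should have no medical or psychiatric history, which the protocol does not require, just before asking about that history

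*Combined protocol and SAP*

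**What the plan says.** Appendix F is a letter and short questionnaire sent to a collateral contact in the site principal investigator's name. Before any question it states: "To qualify for the study, participants are expected to be free of any medical or psychiatric history". Five yes/no questions follow: history of mental illness, history of medical problems ("have any history of medical problems? Y / N"), problems with cannabis, problems with other substances, and any reason not to take part. The mental-illness and medical questions each ask for an explanation of a yes.

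Section 9.3 makes naming such a person a condition of entry, prefers a relative or partner, and says the contact will provide collateral "information that will be used to determine the participant's eligibility". It adds that the contact may help to corroborate what the participant reports. Section 11.4.1 lists the contact among the steps that reduce risk: "An outside informant specified by the participant will be contacted to confirm the history. This process should screen out unsuitable participants".

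The eligibility rules themselves are narrower than the letter:

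- Section 6.1, item 9: "Physically healthy i.e., no clinically unstable medical conditions at the discretion of the investigator".
- Section 10.4.2: "Participants with stable, chronic, nonemergent, well-controlled conditions may be permitted to participate at the discretion of the site investigator".
- Section 10.4.3: "Participants with stable, chronic, nonemergent, well-controlled psychiatric conditions may be permitted to participate at the discretion of the site investigator e.g., anxiety disorder".
- Section 6.2, item 9a: "Individuals who meet criteria for current major depression at a mild severity* may be included at the discretion of the site principal investigator".
- Section 6.2, item 12 makes an exception for people already treated for stable insomnia or depression.

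**The concern.** An informant is useful because that person can report what the participant leaves out. The value depends on the informant not knowing which answer helps the participant. Appendix F gives that answer away immediately before the first two questions, to someone the participant chose and who is likely to be close to them. The answer it gives is also wrong under the protocol.

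Two things are at stake. The form misstates the trial's eligibility standard to a third party. It also weakens, by an unknown amount, an outside check on exclusions that objective tests do not reveal. The clearest example is Section 6.2, item 10, a lifetime history of bipolar disorder or any psychotic disorder.

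**Working it through.** There is no figure in the plan to reproduce and no arithmetic applies. The check is a comparison of texts in three steps.

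**Step 1. Is the letter's statement true under the protocol?**

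| Source | Standard | Agrees with Appendix F? |
|---|---|---|
| Appendix F | No medical or psychiatric history of any kind | n/a |
| 6.1 item 9; 6.2 items 1 and 2 | Bars unstable medical disorders and clinically significant laboratory abnormalities | No |
| 10.4.2 | Stable, controlled medical conditions allowed at the site investigator's discretion | No |
| 10.4.3 | The same for psychiatric conditions, with anxiety disorder as the example | No |
| 6.2 item 9a | Mild current major depression allowed at discretion | No |
| 6.2 item 12 | Existing treatment of stable insomnia or depression excepted | No |
| 6.2 item 10 | Lifetime bar, for bipolar and psychotic disorders only | No; specific diagnoses |
| 11.4.1 | Screening aims to exclude significant problems | No |
| Appendix E checklist | Repeats inclusion item 9, the mild-depression allowance and the item 12 exceptions | No |

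No criterion matches the letter, and several contradict it. Section 10.4.3 also lists current major depressive disorder as disallowed, which conflicts with item 9a of Section 6.2. Those two places must be reconciled, but the conclusion does not depend on how, because other stable medical and psychiatric history is allowed either way.

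**Step 2. Do the answers matter?** Yes. Section 9.3 uses them for eligibility and for corroboration, and Section 11.4.1 counts the informant as part of risk mitigation. Appendix F is the form Section 9.3 cites for this purpose.

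**Step 3. Where could lost candour matter?** This depends on what else covers the same ground.

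- Current medical state: laboratory tests, ECG and physical and neurological examination (Section 9.5.2) do not depend on the informant.
- Recent use of other drugs: the 12-panel urine test (Section 10.2.1) does not depend on the informant either. The disputed sentence also does not mention substance use.
- Past psychiatric history: the phone screen (Appendix C), medical and psychiatric history, SCID and PRISM (Section 9.5.1) and the psychiatrist's evaluation (Section 11.4.1) draw largely on the participant's own account. Here the informant is the scheduled outside source.

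The leading prompt therefore bears mainly on the third group.

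**The case against.** The strongest reply is that this is loose lay wording with little consequence. The letter speaks of an expectation, not an absolute bar. It invites an explanation of a yes on mental illness and on medical problems, and it ends with an open question about any reason not to take part. An informant could reasonably see that a yes will be weighed. Screening has many other parts, the criteria are reviewed again at Week 1 (Section 9.6.1), and the site principal investigator makes the final decision (Section 5.2). No document reports how informants behave, so reduced candour is an inference.

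Most of this stands, and it limits the point. It does not make the sentence true, and it does not justify stating the favoured answer before the question.

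A reader might infer more than the documents support:

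- *That a yes ends the participant's chance of entry.* The letter does not say so, and its request for an explanation points the other way.
- *That nobody could qualify, since all participants have cannabis use disorder.* The letter asks about cannabis in a separate question, so an informant would not naturally count it as the psychiatric history meant.
- *That a false no would by itself put an excluded person on study drug.* The other screening steps would also have to miss the history.
- *That Section 11.4.1 makes the informant decisive.* Its closing sentence refers to the whole screening process described there, including the structured interview, the psychiatrist's evaluation, laboratory tests and ECG.
- *That sites would apply the letter's standard.* The letter is addressed to the informant. Sites decide on Section 6 and the Appendix E checklist, which carries the correct allowances.

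**Conclusion.** The point holds as an internal contradiction on a form in use, combined with a leading prompt. That the statement is untrue follows directly from the documents. That it can reduce candour is a judgement from the order of the form and the choice of informant. It assumes that some informants know of relevant history and want the participant to be accepted.

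The size cannot be stated. The documents give neither the frequency of undisclosed excluding history nor the rate at which informants disclose it, so any count of missed cases would only restate the rates assumed. The effect is bounded by the other screening steps and falls mainly on lifetime psychiatric history. The primary endpoint, randomization, sample size, alpha and analysis are unaffected. The change is worth making because it is nearly free and the form serves a safety check.

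**What to change.** Delete the sentence in Appendix F and replace it with neutral wording, for example: *We are asking a few questions to help confirm the participant's history; please answer as fully as you can.* The replacement should not indicate which answers affect eligibility. Substituting an accurate summary of the criteria would correct the statement but would still lead the informant. Keep the five questions and the requests for explanation, and leave eligibility to Sections 6.1 and 6.2. When the text is next amended, reconcile Section 10.4.3 with item 9a of Section 6.2 on current major depression.

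The cost is a routine IRB submission for the one-sentence change in Appendix F. That change adds no contact or staff time and alters no eligibility rule.
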